The effects of E+shots on mood, cognitive function, heart rate, blood pressure, cortisol and fine motor task performance NCT #16-05

*Design:* This is a double blinded cross-over experiment with repeated measures on treatment (25mg caffeine vs 100mg caffeine vs e+shots) and Time (Time 1 (pre-beverage), Time 2, Time 3, Time 4). Previous night's sleep and occupation may be used as a co-variate in the statistical analysis.

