#### Procedure:

### Screening day:

- Potential subjects will complete an initial online screening using questionnaires that will be posted on surveymonkey.com. The appendices listed below are the questionnaires that are posted in the survey.
- The survey may be accessed through the tiny URL, QR code, or through a link that will be provided by the researcher.
  - o Appendix G- A demographic and medical history questionnaire
    - As seen in the exclusion criteria all subjects who use prescription or over the counter medications for chronic medical conditions will not be allowed to participate in the study, with the exception of people taking oral contraceptives.
    - Subjects who are taking a prescription or over the counter medication for an acute health condition may be asked to participate in the study after they are no longer taking the medication or they will be given the option to drop out of the study.
  - Appendix H- Profile of Mood Survey (POMS) brief form
    - We will calculate the energy score of the POMS.
    - If the energy score is >=13 then the potential subject will be eliminated from the study
  - o Appendix I- Caffeine consumption questionnaire
    - Using the data from this survey subjects who consume >=200mg of caffeine per day will be eliminated from this study
  - Appendix J- Food frequency questionnaire
    - Using the data from this survey subjects who consume >=150 servings of polyphenols per month will be eliminated from the study
  - Appendix K- Mental and Physical State and Trait Energy and Fatigue Scales (see appendix R for approval to use questionnaire)
    - The objective of this scale is to control of cognitive bias by asking questions regarding use of prescription drugs and using a different energy and fatigue scale to measure energy levels.
    - A score of >10 on the energy scale will eliminate the potential subject
    - This scale also measures physical and mental activity levels which will be used in the statistical analysis as covariates
  - Appendix L- Pittsburgh sleep quality index
    - This survey will be used to measure sleep time and sleep quality of potential subjects.
    - Sleep will be used to determine eligibility on day of testing
    - Sleep quality will be used as a covariate in the statistical analysis
- After completion of survey, a research assistant will verify that the subject is eligible for the study and will contact them via the email that is provided by the subject.

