### Day 1: Familiarization day

To reduce experimental error that may occur due to learning effect, subjects will be asked to come in for approximately 40 minutes to familiarize themselves with the protocol. This time will also be used to confirm their

eligibility by confirming the accuracy of the information entered in the initial screening questionnaires, obtain informed consent and begin the procedure. The following will be the procedure for the day:

- We will measure subjects' height and weight using a stadiometer and scale, as well as BP. We will
  eliminate subjects who have a BMI >30.0 and resting systolic BP >140mmHg or resting diastolic BP
  >90mmHg.
- Subjects will then go through a test battery of:
  - Computerized cognitive battery (see appendix V for description):

•	Serial subtraction of the number three	2 minutes
•	Serial subtraction of the number seven	2 minutes
•	Continuous performance test (CPT)	5 minutes
•	Bakan rapid visual processing task	16 minutes

Self-reported measures (see Appendix N, O, H)

Motivation to perform cognitive tasks
 Visual analog scales of mental energy and fatigue
 Profile of Mood State fatigue and vigor scales
 3 minutes

Physiological measures

Resting heart rate and blood pressure 1 minute

Fine motor skills

9-hole peg test5 minutes

Total time 36 minutes

Subjects who are excluded or choose to drop out on this date will not receive the \$5 compensation.

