### Days 2-4

Testing days 2-4 will be similar except subjects will consume a different beverage daily (list the 3 different beverages). To reduce bias, the days that subjects will consume a certain beverage will be randomized using a randomizing software on randomizer.org. All beverages are labeled as products, A, B or C and are blinded for the researcher. Information regarding all beverages is listed in Table 1.

On each day subjects will complete the following procedure:

Subjects will complete a pre-screening questionnaire on each day. The questionnaire will contain the following surveys

- Appendix M- 24 hour drug/medicine/supplement recall
  - This survey asks for a 24-hour prescription medication, over the counter medication, and supplement recall. Because of the potential for cognitive bias (as described above) we are asking the subjects for the names of any medications they may be taking. In our past studies there were a few subjects that initially reported that they were not taking any prescription or over the counter medications (either for a chronic or acute health condition) however, during the daily testing procedures when we asked these subjects specifically what medications they were taking they listed certain medications. By asking specifically what medications the subjects are taking we are hoping to reduce the risk of cognitive bias and appropriately eliminate subjects who are taking prescription or over the counter medications while they are in the study.
    - The survey asks if subjects are taking an oral contraceptive and specifically what the name of the oral contraceptive is. The information on the specific type of oral contraceptive is needed as certain oral contraceptives have an impact on mood while others do not (Kahn & Halbriech, 2005).
  - We are also asking for caffeine intake and time of intake. To control for cognitive bias we are asking for time of intake.
- Appendix N- Sleep questionnaire
  - o This survey will be used to determine the amount of sleep the subject had the night before.
  - This survey will serve two purposes
    - If subjects had > or < ±2 hours of sleep from their normal sleep then they will be rescheduled. Their normal sleep will be determined using Appendix L. Their normal sleep will be given to the researcher in charge of collecting data prior to subject's arrival.

- If the subject is eligible for the study, the sleep may be used as a covariate in the data analysis.
- Appendix Q- What I ate today

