# Analysis of outcomes:

Hypothesis will be tested using a two factor (3 beverages x 4 times) repeated measures ANCOVA on change scores (Times 4, 3 and 2 minus Time 1 are the 4 Times). The primary interest will be whether there is a statistically significant main effect for time or interaction. Focused contrasts between specific time points as follow up tests.

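### The primary interest includes the time main effect, which cannot separate e+shots from a comparator, while the beverage main effect and between-beverage contrasts are not named

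*Combined protocol and SAP*

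**What the plan says.** The title gives the aim as "The effects of E+shots on mood, cognitive function, heart rate, blood pressure, cortisol and fine motor task performance". The Design paragraph describes a double-blind cross-over with "repeated measures on treatment (25mg caffeine vs 100mg caffeine vs e+shots) and Time (Time 1 (pre-beverage), Time 2, Time 3, Time 4", and under Days 2-4 "the days that subjects will consume a certain beverage will be randomized using a randomizing software on randomizer.org". The study is therefore built to compare beverages within subjects.

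Analysis of outcomes is one short paragraph. It specifies a two-factor repeated measures ANCOVA (three beverages by four times) on change scores, and defines the time factor as "Times 4, 3 and 2 minus Time 1 are the 4 Times", although that phrase lists three differences. The effects of interest are given as "The primary interest will be whether there is a statistically significant main effect for time or interaction". The follow-up is "Focused contrasts between specific time points as follow up tests". Neither the beverage main effect nor a contrast of e+shots with a comparator is named anywhere. No sample size, SD, effect size or significance level is stated.

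**The concern.** The study asks whether e+shots differs from the comparators, but one of the two effects of primary interest contains no comparison of beverages. Because the two are joined by an or, a time effect alone satisfies the statement.

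A time effect shared by all beverages is plausible here. Table 2 puts four 36-minute batteries into 194 minutes, with 10-minute rests between the last three. Fatigue, remaining practice, or a response common to all three drinks would each produce one. The familiarization day is planned "To reduce experimental error that may occur due to learning effect", which may reduce practice but does not address fatigue or a shared response.

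Two things are at stake. Change common to all beverages could be reported as the result of primary interest. And, depending on how Time is coded, a sustained e+shots effect could fall in a term that was not singled out in advance.

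**Working it through.** The plan gives no power figure or sample size to reproduce, so the check is structural first and numerical second.

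**Step 1: what each effect compares.** Write the mean for beverage b at time t as m(b,t).
- Time main effect: compares the average of m(b,t) over the three beverages between times. It involves no difference between beverages.
- Interaction: asks whether beverage differences change across the levels of Time. It does compare beverages.
- Beverage main effect: compares the average of m(b,t) over times between beverages. It is in the model but not named as of interest.

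**Step 2: why the number of time levels matters.** Suppose e+shots adds a constant d at Times 2, 3 and 4.
- Three change scores: the profile for e+shots is (d, d, d) and for the others (0, 0, 0). The beverage difference does not change over time, so the interaction component is exactly zero and the whole effect is in the beverage main effect.
- Time 1 kept as a fourth level: the e+shots profile is (0, d, d, d). The difference changes between Time 1 and the rest, so the interaction responds.

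**Step 3: illustrative size.** Assumptions, none from the documents: n = 30, within-subject variance 1, of which 0.3 is day-level and 0.7 residual, two-sided alpha 0.05, no covariates. Power comes from the noncentral F distribution with noncentrality λ.

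*Identical beverages, shared drift δ per battery, time main effect.* λ = n × 3 × δ² × k / 0.7, where k is the sum of squared deviations of equally spaced times: k = 2 for three levels, k = 5 for four. The sign of δ does not matter.

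| δ | Levels | λ | df | Time effect significant |
|---|---|---|---|---|
| 0.15 | 3 | 90 × 0.0225 × 2 / 0.7 = 5.79 | 2, 58 | 54% |
| 0.15 | 4 | 90 × 0.0225 × 5 / 0.7 = 14.46 | 3, 87 | 89% |
| 0.05 | 3 | 90 × 0.0025 × 2 / 0.7 = 0.64 | 2, 58 | 10% |
| 0.05 | 4 | 90 × 0.0025 × 5 / 0.7 = 1.61 | 3, 87 | 16% |

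Simulation agrees (54-55% and about 90% at 0.15; 10% and 16% at 0.05). In the same runs, tests that compare beverages reject at about the nominal 5%.

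*Real e+shots effect, no drift.* With one of three beverages shifted, the between-beverage sum of squares carries a factor 2/3.
- Steady +0.5 SD, three-level interaction: λ = 0, rejection 5%.
- Steady +0.5 SD, four-level interaction: λ = 30 × 0.25 × (2/3) × (3/4) / 0.7 = 5.36 on 6 and 174 df, about 35% (simulated 34%).
- Steady +0.5 SD, beverage effect on change scores: the variance of the mean change is 0.7/3 + 0.7 = 0.933; λ = 30 × 0.25 × (2/3) / 0.933 = 5.36 on 2 and 58 df, about 51% (simulated 50%).
- Waning +1.0, +0.5, 0 SD, three-level interaction: the squared deviations from the mean of 0.5 sum to 0.5; λ = 30 × 0.5 × (2/3) / 0.7 = 14.29 on 4 and 116 df, about 86%.
- Waning effect, beverage effect on change scores: the mean is again 0.5, so power is as in the steady case (51%; simulated 52%).

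**Step 4: covariates.** The plan is an ANCOVA; for example, "Sleep quality will be used as a covariate in the statistical analysis". In simulation at n = 20 and drift -0.15, adding 3 or 5 centred subject-level covariates moved the time test by at most 1.3 percentage points. A covariate that is constant within a day, entered additively, cancels from the time test. Covariate adjustment does not alter the finding.

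**The case against.** The strongest defence is that the interaction is named and is a genuine between-beverage test. A single drink followed from minute 36 to minute 194 may well act unevenly over time, and for the waning effect above the three-level interaction (about 86%) clearly beats the beverage main effect on change scores (about 52%). The documents give no reason to treat a steady effect as the default. This stands, and it rules out the reading that the plan has no test capable of showing a beverage difference.

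A reader might also infer that the beverage effect is left out of the analysis. It is not: the two-factor model contains it, and the Design paragraph makes treatment a factor. The gap is in what is singled out in advance. The follow-up wording does not say whether the time-point contrasts are made within or between beverages, so between-beverage contrasts are unnamed rather than excluded.

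Nor is there a formal success rule. The text speaks of primary interest, and separately reported tests would let a reader see a time effect without an interaction. Treating the two as a single pass/fail criterion goes beyond the text.

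Finally, one might conclude that meeting the stated interest says little about whether e+shots works. That holds only for particular inputs. At n = 30 with Time 1 kept and a steady +0.5 SD effect, time or interaction is significant in about 90% of trials without the effect and 75% with it at drift -0.15 SD. At drift -0.05 SD the figures are 20% and 43%, and at +0.15 SD 91% and 99%. For the waning effect without drift, the rate rises from 10% to 95-98%.

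None of this rescues the time main effect as an effect of primary interest, or supplies a named contrast of e+shots with either comparator.

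**Conclusion.** The point holds in this form. The time main effect cannot show that e+shots differs from a comparator, whatever the sample size, variance or coding of Time; that part needs no assumption. The named interaction can show a difference, but under three-level coding it has no power beyond its 5% error rate for an effect constant over Times 2 to 4. Under four-level coding it detects such an effect with less power than a beverage test (about 34% against 50% in the illustration). Even a significant interaction needs between-beverage contrasts to show which beverage differs.

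The percentages rest entirely on assumed inputs and show direction and rough scale only. How often a shared time effect would appear depends strongly on the drift: from about 10% to about 90% over the values shown. The correction should be made before unblinding, because it concerns the study's central inference and costs almost nothing.

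**What to change.** Reword the Analysis of outcomes paragraph:

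- **(a)** Remove the time main effect from the primary interest and report change over time descriptively, by beverage.
- **(b)** Before unblinding, name one primary test that compares beverages: either the beverage effect over Times 2 to 4 adjusted for that day's Time 1 score, or beverage by time with Time 1 kept as a level.
- **(c)** State whether Time has three or four levels.
- **(d)** Add planned contrasts of e+shots with each of the two comparators, adjusted for the two comparisons (Holm, for example).

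No new measurements are needed. The sponsor gives up the option of presenting a time effect as a primary result. Neither choice in (b) is more powerful for every effect shape. In simulation at n = 30, with test-day terms in both models, the adjusted beverage effect had 82% power against 33% for beverage by time when the effect was a steady +0.5 SD, and 82% against 92% when it was +1.0, +0.5, 0 SD. The choice should follow the time course that the sponsor expects. Whether the trial is large enough for either cannot be judged, since no sample size is given.
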